Appendix 3**Criteria for Potentially Clinically Significant Vital Sign Abnormalities**

Variable	Criterion Value^a	Change Relative to Baseline^a
Heart Rate	> 110 bpm < 50 bpm	≥ 15 bpm increase ≥ 15 bpm decrease
Systolic Blood Pressure	> 160 mmHg < 90 mmHg	≥ 20 mmHg increase ≥ 20 mmHg decrease
Diastolic Blood Pressure	> 105 mmHg < 50 mmHg	≥ 15 mmHg increase ≥ 15 mmHg decrease
Weight	Not Applicable	≥ 5% increase ≥ 5% decrease
Respiratory Rate	< 12 breaths/min or > 20 breaths/min	Not Applicable
Temperature	< 36°C or > 38°C	Not Applicable

^aIn order to be identified as potentially clinically relevant, an on-treatment value must meet the “Criterion Value” and also represent a change from the subject’s baseline value of at least the magnitude shown in the “Change Relative to Baseline” column.

OPC-167832

Study 323-201-00007

Appendix 4 Definition of Grades for Vital Sign in the Division of AIDS Table¹ for Grading the Severity of Adult and Pediatric Adverse Events

The table below contains some of the criteria provided in the DAIDS table. Please see pages of the DAIDS v2.1 tables available in [Appendix 2](#) for details for blood pressure abnormalities, unintentional weight loss, fever.

Abnormality	AGE GROUP	GRADE 1 MILD	GRADE 2 MODERATE	GRADE 3 SEVERE	GRADE 4 POTENTIALLY LIFE- THREATENING
Hypertension (with the lowest reading taken after repeat testing during a visit) Male/Female	≥ 18 years of age	140 to < 160 mmHg systolic OR 90 to < 100 mmHg diastolic	≥ 160 to < 180 mmHg systolic OR ≥ 100 to < 110 mmHg diastolic	≥ 180 mmHg systolic OR ≥ 110 mmHg diastolic	Life-threatening consequences in a participant not previously diagnosed with hypertension (eg, malignant hypertension) OR hospitalization indicated
Unintentional Weight Loss (excludes postpartum weight loss)		NA	5% to < 9% loss in body weight from baseline	≥ 9% to < 20% loss in body weight from baseline	≥ 20% loss in body weight from baseline OR Aggressive intervention indicated (eg, tube feeding, total parenteral nutrition)
Fever (non-axillary temperatures only)		38.0°C to < 38.6°C or 100.4°F to < 101.5°F	≥ 38.6°C to < 39.3°C or ≥ 101.5°F to < 102.7°F	≥ 39.3°C to < 40.0°C or ≥ 102.7°F to < 104.0°F	≥ 40.0°C or ≥ 104.0°F

OPC-167832

Study 323-201-00007

Appendix 5 Criteria for Identifying ECG Measurements of Potential Clinical Relevance

Category Diagnosis	Criterion Value ^a	Change Relative to Baseline ^a
Rate		
Tachycardia	110 bpm	increase of 15 bpm
Bradycardia	50 bpm	decrease of 15 bpm
Rhythm		
Sinus tachycardia ^b	110 bpm	increase of 15 bpm
Sinus bradycardia ^c	50 bpm	decrease of 15 bpm
Supraventricular premature beat	All	not present → present
Ventricular premature beat	All	not present → present
Supraventricular tachycardia	All	not present → present
Ventricular tachycardia	All	not present → present
Atrial fibrillation	All	not present → present
Atrial flutter	All	not present → present
Conduction		
1° atrioventricular block	PR > 0.20 s	not present → present
2° atrioventricular block	All	not present → present
3° atrioventricular block	All	not present → present
Left bundle-branch block	All	not present → present
Right bundle-branch block	All	not present → present
Pre-excitation syndrome	All	not present → present
Other intraventricular conduction block ^d	QRS > 0.12 s	increase of 0.02 s
Infarction		
Acute or subacute	All	not present → present
Old	All	not present → present 12 weeks post trial entry
ST/T Morphological		
Myocardial Ischemia	All	not present → present
Symmetrical T-wave inversion	All	not present → present
Increase in QT	QT > 450 msec (males and females)	-
	QT > 480 msec (males and females)	-
	QT > 500 msec (males and females)	-
Increase in QTcF	QTcF > 450 msec (males and females)	-
	QTcF > 480 msec (males and females)	-
	QTcF > 500 msec (males and females)	-
		Increase of ≥ 30 msec and ≤ 60 msec
		Increase of > 60 msec
Increase in QTcB	QTcB > 450 msec (males and females)	-

OPC-167832

Study 323-201-00007

Category Diagnosis	Criterion Value ^a	Change Relative to Baseline ^a
	QTcB > 480 msec (males and females)	-
	QTcB > 500 msec (males and females)	-
		Increase of ≥ 30 msec and ≤ 60 msec
		Increase of > 60 msec

^aIn order to be identified as potentially clinically relevant, an on-treatment value must meet the “Criterion Value” OR represent a change from the subject’s baseline value of at least the magnitude shown in the “Change Relative to Baseline” column.

^bNo current diagnosis of supraventricular tachycardia, ventricular tachycardia, atrial fibrillation, atrial flutter, or other rhythm abnormality.

^cNo current diagnosis of atrial fibrillation, atrial flutter, or other rhythm abnormality.

^dNo current diagnosis of left bundle branch block or right bundle branch block.

OPC-167832

Study 323-201-00007

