- 13) Exposure to any substances known to stimulate hepatic microsomal enzymes within 30 days prior to the screening visit (eg, occupational exposure to pesticides, organic solvents).
- 14) Use of tobacco products, nicotine replacement therapies, e-cigarettes, or daily exposure to second-hand smoke within 2 months prior to the screening visit, urine cotinine concentrations > 200 ng/mL, or serum cotinine concentrations > 20 ng/mL, at the screening visit or at check-in.
- 15) Subjects who have supine blood pressure, after resting for at least 5 minutes, > 140 mmHg or < 100 mmHg (systolic blood pressure) or > 90 mmHg or < 50 mmHg (diastolic blood pressure) at the screening visit or check-in. If the blood pressure is outside of the specified ranges but is not deemed clinically significant, a total of 3 readings will be taken 10 minutes apart. The subject will be included in the trial if 2 out of 3 readings are within the specified ranges.
- 16) Abnormal ECG findings at screening or check-in, as follows:
 - a) A QTcF > 450 msec (males) or QTcF > 470 msec (females).
 - b) QRS interval > 120 msec.
 - c) PR interval > 200 msec.
- 17) Subjects who have a supine heart rate, after resting for at least 5 minutes, outside the range of 50 to 90 beats per minute at the screening visit or at check-in. If the heart rate is outside of the specified range but is not deemed clinically significant, a total of 3 readings will be taken 10 minutes apart. The subject will be included in the trial if 2 out of 3 readings are within the specified range.
- 18) Any subject who, in the opinion of the investigator, should not participate in the trial.
- 19) Female subjects who are breast-feeding or who have a positive pregnancy test result prior to receiving IMP.

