10.6 Electrocardiogram Data

Electrocardiogram measurements (will include HR, PR, QRS, RR, QT, QTcF, QTcB) and mean changes from baseline will be summarized by part and time point. The incidence of potentially clinically significant changes and abnormalities in ECG evaluations will be summarized. Electrocardiogram data will be presented in listings. In ECG listings, abnormal will also indicate whether CS or not. For ECG assessments, baseline is defined as the average of triplicate (if not collected as triplicate, then single, or duplicate values will be averaged) ECG values collected at check-in for each Part. If there are two or more sets of ECG (check-in) evaluations prior to first IMP dosing, the last set of triplicate (or duplicate or single, as applicable) will be averaged for presenting as the baseline values (whether these are scheduled or unscheduled). Predose ECGs will be reported as predose and are not part of the baseline assessments.

If the baseline value is missing, it will not be imputed.

ECG parameter values will be reported as received in the raw data. ECG data will be reported out in listings, with the actual value and change-from-baseline value included in the listing.

Averaged ECG parameters will be rounded down to the nearest integer for easy interpretability.

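### The ECG relevance rule joins limit and change with OR in every row, so heart-rate and QRS changes within the normal range, and findings already present at baseline, enter the incidence table.

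*SAP*

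**What the plan says.** SAP Appendix 5 has a criterion column and a change-from-baseline column. Footnote a makes an on-treatment value potentially clinically relevant if it meets the first "OR represent a change from the subject’s baseline value of at least the magnitude shown" in the second. It names no rows to which this is limited.

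- **Rate and sinus rhythm:** 110 bpm with "increase of 15 bpm", and 50 bpm with a fall of 15 bpm.
- **Other intraventricular conduction block:** QRS above 0.12 s, with an increase of 0.02 s.
- **Most rhythm, conduction, infarction and ST/T findings:** criterion 'All', with change "not present → present".
- **QT, QTcF, QTcB:** limits on their own lines with no change value; for QTcF and QTcB, increases on their own lines with no limit.

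SAP 10.6 states: "The incidence of potentially clinically significant changes and abnormalities in ECG evaluations will be summarized". It adds no treatment-emergent condition, whereas SAP 10.4 does for vital signs. Appendix 3 uses heart-rate limits of above 110 and below 50 bpm with changes of at least 15 bpm, but its footnote says the value must meet the criterion "and also represent a change from the subject’s baseline value of at least the magnitude shown" in the change column. For ECGs, "baseline is defined as the average of triplicate" values at check-in.

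**The concern.** In a row that names one diagnosis and fills both columns, the natural purpose is to find values that are abnormal and have also moved. OR removes that purpose in two ways. A change wholly inside the normal range is enough for a label such as tachycardia, bradycardia or conduction block. Where the criterion is 'All', every occurrence qualifies, so the new-onset column has no effect.

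ECGs belong to the secondary safety endpoint, and each part has 12 subjects, so a few chance flags visibly change an incidence table. The same heart-rate change can also be flagged in the ECG table and not in the vital-sign table, with no reason given.

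**Working it through.** The plan states no figure to reproduce. The check applies the rule as written, then illustrates its size.

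**1. The rule applied to cases** (limits read as ≥110 and ≤50 bpm, since Appendix 5 shows no direction)

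| Baseline → on treatment | OR (Appendix 5) | AND (Appendix 3 connector) |
|---|---|---|
| 60 → 75 bpm | tachycardia | not flagged |
| 60 → 74 bpm | not flagged | not flagged |
| 90 → 75 bpm | bradycardia | not flagged |
| 95 → 110 bpm | tachycardia | tachycardia |
| 50 → 50 bpm | bradycardia | not flagged |
| QRS 0.08 → 0.10 s | conduction block | not flagged |
| 'All' finding: absent → present | flagged | flagged |
| 'All' finding: present → present | flagged | not flagged |

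**2. What eligibility implies.** Protocol 5.2.2, criterion 17, sets an entry heart rate of 50 to 90 bpm. For a baseline in that range, a 15 bpm rise is reached at 65 to 105 bpm, always below 110. Any value of 110 or more is already a rise of at least 110 − 90 = 20 bpm. The 110 bpm limit therefore adds no flag, and the tachycardia row reduces to a rise of 15 bpm.

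**3. Number of ECGs after the first dose** (Protocol Tables 1.3-1 and 1.3-2, ECG footnotes)

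- Part 1: Day 1 at 3 h, Day 2, Day 15 predose and 3 h, Day 16, Day 26 = 6.
- Part 2: Day 1 at 3 h, Day 2, Day 8 predose and 6 h, Day 9, Day 14 predose and 6 h, Day 15, Day 25 predose and 3 h, Day 26, Day 32 = 12.

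**4. Chance flags with no drug effect.** Assumptions: within-subject SD s of 4 to 8 bpm, normal and independent readings, differences rounded to whole bpm. Only the change limb is counted, in either direction. The difference from baseline has SD s√2 for a single-reading baseline, and s√(1 + 1/3) for the mean of three independent readings. With rounding, a flag needs a difference of at least 14.5.

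For one ECG at s = 6:

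- single baseline: 14.5 / 8.49 = 1.71, two-sided probability 8.7%
- triplicate: 14.5 / 6.93 = 2.09, two-sided probability 3.6%

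The ECGs of one subject share a baseline, so the chance of at least one flag was simulated (200,000 subjects):

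| s (bpm) | Part 1 triplicate | Part 1 single | Part 2 triplicate | Part 2 single |
|---|---|---|---|---|
| 4 | 1% | 5% | 2% | 9% |
| 5 | 7% | 17% | 12% | 27% |
| 6 | 19% | 33% | 32% | 49% |
| 7 | 34% | 49% | 54% | 67% |
| 8 | 49% | 62% | 72% | 81% |

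Triplicates taken at one sitting are probably correlated, so the truth lies between the columns. Out of 12 subjects the extremes are 0.1 to 7.4 in Part 1 (12 × 0.01 to 12 × 0.62) and 0.2 to 9.7 in Part 2 (12 × 0.02 to 12 × 0.81). Rises alone give about 0.5 to 32% and 1 to 43%.

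**5. The same under AND.** Tachycardia flags are below 0.1% throughout. Bradycardia flags do not vanish at low resting rates: at a mean of 60 bpm and s of 5 to 8, about 4 to 25% (Part 1) and 7 to 40% (Part 2) remain. Those are values at or below the 50 bpm limit with a fall of at least 15 bpm.

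**6. 'Old' infarction.** Its change column adds 12 weeks after trial entry, or 84 days. Even from the start of screening (Day −28), the last scheduled ECG (Day 26 or 32) comes at most 28 + 32 = 60 days later. Under AND this row could not be met on schedule.

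**The case against.** The strongest defence is that OR is deliberate: a sensitive screen, capitalised, in an appendix that the SAP history shows was revised. The QT rows do need OR. This stands for those rows, but the documents give no reason for carrying it to rows with both columns filled. Appendix 3 is no clean model either: its connector cannot be met literally for weight, respiratory rate or temperature, where one column is not applicable.

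The baseline problem is also narrow. Eligibility requires good health by ECG and excludes PR above 200 msec, QRS above 120 msec and clinically significant cardiac history. What remains is mainly premature beats and T-wave changes.

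A reader might infer three stronger things that the documents do not support:

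- **That old findings are reported as new.** The label is potentially clinically relevant. Old and new findings are mixed, not relabelled.
- **That a real signal could not be told from noise.** SAP 10.6 also gives mean changes, listings with values and changes, and a clinical-significance marker. Protocol 8.5.4 requires clinically significant abnormalities to be recorded as adverse events.
- **That the table would fill with false conduction block.** The rule permits it, but no QRS variability is given and no rate has been computed.

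A missing inequality sign at 110 and 50 bpm may be a loss in PDF reading, so it is a point to confirm rather than a proven omission.

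**Conclusion.** The point holds in this limited form. As written, footnote a flags heart-rate and QRS changes inside the normal range and makes the new-onset condition redundant wherever the criterion is 'All'. It also classifies the same heart-rate change differently from Appendix 3.

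The size is uncertain. It runs from negligible at an SD of 4 bpm with a triplicate baseline to most Part 2 subjects at 8 bpm with a single-reading baseline. It rests on an assumed SD and on counting a subject once for a flag at any visit, which the SAP does not specify. Flags from the 50 bpm limit itself are left out of these figures and would add to them at low resting rates.

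Only the descriptive ECG incidence table is affected. No stopping or dosing rule in the documents uses these flags. The change is worth making before the tables are produced, but it is not critical to the trial.

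One neighbouring matter should not be attributed to the connector. A woman may enter with QTcF of 451 to 470 msec and then meet the 450 msec line under 'Increase in QTcF' without any increase. That line has no change value, so changing OR to AND would not alter it.

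**What to change.** Rewrite Appendix 5 footnote a row by row and reconcile it with Appendix 3:

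- **Rate, Rhythm, Conduction, Infarction and ST/T morphology rows:** the value must meet the criterion AND the change column.
- **QT, QTcF and QTcB:** each line stands alone. A blanket AND would disable these rows.
- **'Old' infarction:** give it its own wording, because its 12-week condition falls after the last scheduled ECG.
- **110 and 50 bpm:** confirm the direction, and whether the limit itself counts, so that the two appendices agree.

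While reconciling, let the Appendix 3 rows with a 'Not Applicable' column stand on their single condition. The cost is a SAP footnote edit and the matching table programming. No new data are needed, and the primary analysis does not change.

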Appendix 6 Technical Details

The following code illustrates the program statements that could be used to fit the linear mixed effect model using the MIXED procedure in SAS. The independent variable will be treatment (A=OPC-167832 alone, and B=OPC-167832 and itraconazole). Analyses will be performed using the log-transformed PK parameters.

Y denotes the response variable (eg, the log-transformed C_{\max} , AUC_t or AUC_{∞}). The alpha level is set to 0.1 so that a two-sided 90% CI will be produced as model estimation. The standard error for difference is calculated using Satterthwaite approximation for two groups with unequal variance.

```
PROC MIXED CL ALPHA=0.1;

    CLASS SUBJECT TREATMENT ;

    MODEL Y = TREATMENT / DDFM=SATTERTH;

    RANDOM SUBJECT ;

    LSMEANS TREATMENT / CL ALPHA=0.1;

    ESTIMATE 'B VS A' TREATMENT -1 1 / CL ALPHA = 0.1; * Part 1;

RUN;
```

The ESTIMATE statement will be used to obtain the least square estimate of the difference between treatments, the standard error associated with the difference, and the corresponding 90% CI.

The antilog of the differences will then provide an estimate of the geometric mean ratios (GMR; OPC-167832 + potentially interacting drug/OPC-167832 alone), and the antilog of the confidence limits will provide the 90% CIs for the GMRs.

Part 2

The following code illustrates the program statements that could be used to fit the linear mixed effect model using the MIXED procedure in SAS for Part 2 data.

Y denotes the response variable (eg, the log-transformed C_{\max} , AUC_t or AUC_{∞}). (D=OPC-167832 alone, and E=OPC-167832 and carbamazepine). The alpha level is set to 0.1 so that a two-sided 90% CI will be produced as model estimation. The standard error for difference is calculated using Satterthwaite approximation for two groups with unequal variance.

```
PROC MIXED CL ALPHA=0.1;
```

OPC-167832

Study 323-201-00007

```
CLASS SUBJECT TREATMENT ;  
MODEL Y = TREATMENT / DDFM=SATTERTH;  
RANDOM SUBJECT ;  
LSMEANS TREATMENT / CL ALPHA=0.1;  
ESTIMATE 'E VS D' TREATMENT -1 1 0 / CL ALPHA = 0.1;  
RUN;
```

The ESTIMATE statement will be used to obtain the least square estimate of the difference between treatments, the standard error associated with the difference, and the corresponding 90% CI. The antilog of the differences will then provide an estimate of the geometric mean ratios (GMR; OPC-167832 + potentially interacting drug/OPC-167832 alone), and the antilog of the confidence limits will provide the 90% CIs for the GMRs.

This page is a manifestation of an electronically captured signature

SIGNATURE PAGE

Document Name: SAP_007_13Mar2023

Document Number: 1000239960

Signed by	Meaning of Signature	Server Date (dd-MMM- yyyy hh:min) - UTC timezone
PPD	Clinical Approval	21-Mar-2023 19:59:54
PPD	Biostatistics Approval	14-Mar-2023 21:12:01
PPD	Clinical Pharmacology Approval	21-Mar-2023 13:19:22
